6.1.4.1 Performance criteria

6.1.4.1.1 Cornea and conjunctiva staining (Oxford score)

Cornea and conjunctiva staining will be assessed with a slit lamp after instillation of unpreserved fluorescein in the examined eye. In order to optimize the fluorescein staining signal without any masking by the fluorescence quenching effect, 1 drop of fluorescein will be instilled in the examined eye. Cornea and conjunctiva staining is represented by punctate dots on a serie of panels (A-E). Staining ranges from 0-5 for each zone and from 0-15 for the total exposed inter-palpebral conjunctiva and cornea. The dots are ordered on the log scale (Oxford scale) below:

PANEL	Grade	Criteria
A 	0	Equal to or less than panel A
B 	I	Equal to or less than panel B, greater than A
C 	II	Equal to or less than panel C, greater than B
D 	III	Equal to or less than panel D, greater than C
E 	IV	Equal to or less than panel E, greater than D
>E	V	Greater than E
 FROM 0-5	 FROM 0-5	 FROM 0-5
	TOTAL SCORE:	 FROM 0-15

6.1.4.1.2 Ocular Surface Disease Index (OSDI)

The OSDI is assessed on a scale from 0 to 100, with higher scores representing greater disability. The patients will be asked the following 12 questions:

Have you experienced any of the following during the last week?	All of the time	Most of the time	Half of the time	Some of the time	None of the time
1. Eyes that are sensitive to light.	4	3	2	1	0
2. Eyes that feel gritty?	4	3	2	1	0
3. Painful or sore eyes?	4	3	2	1	0
4. Blurred vision?	4	3	2	1	0
5. Poor vision?	4	3	2	1	0
Subtotal score for answers 1 to 5					A

Have problems with your eyes limited you in performing any of the following during the last week ?	All of the time	Most of the time	Half of the time	Some of the time	None of the time	NA
6. Reading?	4	3	2	1	0	NA
7. Driving at night?	4	3	2	1	0	NA
8. Working with a computer or bank machine (ATM)?	4	3	2	1	0	NA
9. Watching TV?	4	3	2	1	0	NA
Subtotal score for answers 6 to 9					B	

Have your eyes felt uncomfortable in any of the following situations during the last week ?	All of the time	Most of the time	Half of the time	Some of the time	None of the time	NA
10. Windy condition?	4	3	2	1	0	NA
11. Places or areas with low humidity (very dry)?	4	3	2	1	0	NA
12. Areas that are air conditioned	4	3	2	1	0	NA
Subtotal score for answers 10 to 12					C	

Add subtotals A, B and C to obtain D (D=sum of scores for all questions answered)	D
--	----------

Total number of questions answered (do not include questions answered NA)	E
--	----------

OSDI is calculated according to the following formula: $OSDI = D \times 25 / E$

6.1.4.1.3 Van Bijsterveld score

The ophthalmologist will realize a colorimetric test with Lissamine green dye. Lissamine green stains dead and degenerate cells, and does not stain healthy epithelial cells. The evaluation will be done from 1 to 4 minutes after the staining.

The ophthalmologist will determine the dry eye severity with the following scales (Van Bijsterveld Score from 0 to 9¹⁾):

Nasal bulbar conjunctiva

0	1	2	3
			
No staining	Confluent staining		

Temporal bulbar conjunctiva

0	1	2	3
			
No staining	Confluent staining		

Cornea

0	1	2	3
			
No staining	Confluent staining		

Total score: / 9

6.1.4.1.4 Schirmer test

The Schirmer test is a method used to evaluate aqueous tear production.

It consists in inserting a strip (measuring 35 by 5 mm), without anaesthesia, over the lower lid margin of the eye during 5 minutes and then measuring the length of paper wetting in millimeters. The results is expressed in mm/5min.

6.1.4.1.5 Tear Break Up Time (TBUT)

The Tear Break Up Time (TBUT) is the measurement of the break-up time of lacrymal film. This is the time needed by the lacrymal film to cover in an homogeneous and coherent way all the ocular surface. TBUT is assessed with slit lamp examination and expressed in seconds.

To measure TBUT, fluorescein is instilled into the patient's tear film and the patient is asked not to blink while the tear film is observed with slit lamp. The TBUT is recorded as the number of seconds that elapse between the last blink and the appearance of the first dry spot in the tear film.

The TBUT will be assessed three times and the sum of these three measurements will be calculated.

6.1.4.1.6 Ocular dryness symptoms

The subjects will score their ocular symptoms (**one global score for both eyes**) on structured scales from 0 to 10. These scales are presented below.

1. Discomfort

0	1	2	3	4	5	6	7	8	9	10
										
None						Very important				

2. Burning / stinging

0	1	2	3	4	5	6	7	8	9	10
										
None						Very important				

3. Eye dryness sensation

0	1	2	3	4	5	6	7	8	9	10
										
None						Very important				

4. Itching

0	1	2	3	4	5	6	7	8	9	10
										
None						Very important				

5. Sandy feeling / Foreign body sensation

0	1	2	3	4	5	6	7	8	9	10
										
None						Very important				

6. Photophobia

0	1	2	3	4	5	6	7	8	9	10
										
None						Very important				

7. Blurred vision

0	1	2	3	4	5	6	7	8	9	10
										
None						Very important				

In case of other symptom(s) declared by the patient, it will be also recorded in the CRF (free text).

The sum of all symptom scores will be calculated to obtain a score from 0 to 70.

6.1.4.1.7 Global treatment performance score

Performance of the treatment will be assessed by the investigator and the patient using the following rating scale:

1. Very satisfactory
2. Satisfactory
3. Not very satisfactory
4. Unsatisfactory

6.1.4.2 Safety criteria

All systemic and ocular adverse events (AE) and adverse device effects (ADE) will be collected and reported by the investigator (see paragraph 14) throughout the study. A daily-log will be given to the subject at each visit in order to write eventual concomitant treatments or adverse events.

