6.1.3.2 Secondary endpoints

- Comparison of D35 versus D0 and D84 versus D0 for each product and comparison between products for the following parameters:
 - Evolution of cornea and conjunctiva staining (Oxford score on a scale) on worse eye.
 - Evolution of OSDI score (Ocular Surface Disease Index).
 - Evolution of Van Bijsterveld score (Lissamine green staining) in worse eye.
 - Evolution of Schirmer test result in worse eye.
 - Evolution of Tear film Break-Up Time (TBUT) in worse eye.
 - Evolution of ocular dryness severity by evaluation of each main symptom by the patient and total score of all symptoms
 - Evaluation of treatment performance by the investigator and the patient.
 - Collection of adverse events and adverse device effects.
- Evaluation of the average frequency of use during 84 days for DM05 and Optive™.

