6.1.5 Timing for assessing and recording the variables

Procedure	Visit 1 Selection visit (D-14 to D-7)	Visit 2 Day 0	Visit 3 Day 35 ± 3 days	Visit 4 Day 84 ± 7 days
	Wash-out period			
	Treatment period			
Written informed consent	●			
Checking of the inclusion and exclusion criteria	●	●		
Medical history, previous and concomitant treatments, demographic data	●			
Urinary pregnancy test for female subjects with childbearing potential		●		●
Distribution of Hydrabak® (NaCl 0.9%)	●			
Inclusion and random assignment		●		
OSDI score	●	●	●	●
Global ocular staining (Oxford score)	●	●	●	●
Schirmer test	●	●	●	●
TBUT	●	●	●	●
Van Bijsterveld score		●	●	●
Symptoms evaluation by the patient		●	●	●
Treatment performance evaluation by the patient and the investigator			●	●
Distribution of treatments by a third person		●	●	
Distribution of a daily-log	●	●	●	
Adverse events recording		●	●	●
Concomitant medication		●	●	●

6.1.6 Equipment to be used for assessing, recording and analysing variables and arrangements for monitoring maintenance and calibration

Each investigator will use his own slit lamp. Dyes (Fluoresceine Faure 0.5% SDU, Lissamine green) and Schirmer strips will be given by the Sponsor.

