6.4 PROCEDURES

6.4.1 Description of all the clinical-investigation-related procedures that patients undergo during the clinical investigation

Selection visit (D-14 to D -7)

- The ophthalmologist will propose to his/her patient to participate to the clinical investigation.
- Information of the patient on study aims and schedule.
- Signature of information sheet and consent form in two copies by the patient and the investigator.
- Collection of previous medical and ophthalmological history, previous and actual treatments, demographic data.
- The ophthalmologist will evaluate the Ocular Surface Disease Index, the global ocular staining (Oxford score) and will realize the Schirmer test and TBUT.
- Checking of inclusion and exclusion criteria.
- If the patient is eligible, distribution of Hydrabak® to be used three times per day in both eyes until the inclusion visit, as well as a daily log to write eventual concomitant treatments and adverse events.

Inclusion visit (D0)

- The patient will bring back the Hydrabak® and the daily-log completed.
- Collection of adverse events and concomitant treatments.
- The ophthalmologist will evaluate the Ocular Surface Disease Index, the global ocular staining (Oxford score) and will realize Schirmer test and TBUT.
- Checking of inclusion and exclusion criteria.
- If the patient is eligible, inclusion of the patient and attribution of a randomization number.
- The ophthalmologist will evaluate the Van Bijsterveld score.
- The patient will evaluate his/her ocular symptoms.
- A third person will distribute the treatment according to the randomization list and explain the mode of use of the treatment, as well as a daily log to write eventual concomitant treatments and adverse events

D35

- The patient will bring back the treatments (used and non-used) and the daily-log completed.

- Collection of adverse events and concomitant treatments.
- The ophthalmologist will evaluate the Ocular Surface Disease Index, the global ocular staining (Oxford score), the Van Bijsterveld score and will realize Schirmer test and TBUT.
- The patient will evaluate his/her ocular symptoms.
- The patient and the investigator will evaluate the treatment performance on a 4-point scale.
- A third person will distribute the treatment according to the randomization list and remain the patient about the mode of use, as well as a daily log to write eventual concomitant treatments and adverse events.

D84

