10.4 CORRECTIVE AND PREVENTIVE ACTIONS AND PRINCIPAL INVESTIGATOR DISQUALIFICATION CRITERIA

If major deviations from an investigator are observed during monitoring, the CRA will warn the investigator of the importance to respect the CIP. An investigator who continuously violates the CIP despite CRA warnings could be excluded from the investigation after agreement of the Sponsor.

11- DEVICE ACCOUNTABILITY

The IMD should only be dispensed only under the supervision of a physician approved for the study. The Investigator (or delegate) is responsible for dispensing the study products to the patients who are randomised in the study. The study devices must not be administered to patients who are not randomised in the study.

A preprinted accountability form provided by the CRO must be kept current and must identify the subject number/the number of the IMD dispensed, and the amount of IMD dispensed to and returned by each subject at each visit, with the corresponding dates.

All IMD supplies (empty containers, as well as partly used and unused IMD) must be available for inspection at every monitoring visit. The CRA or Sponsor delegate should verify the investigational site's

Horus Pharma	CIP #15E1122	Final Version 4.0 Date: 04/09/2017	Confidential Page 36/53
--------------	--------------	---------------------------------------	----------------------------

products accountability records against record of administrated doses in the CRF. All used and non-used products will be destructed after signature of the clinical report.

12- STATEMENTS OF COMPLIANCE

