7.5 Follow-up analyses

Will be described at each follow-up visit, by treatment group, on the ITT population only:

- Product and document dispensation (D35 and D84)
 - o Average posology
 - o Posology precision
 - o Frequency of use
 - o Frequency precision
- Pregnancy test (women with childbearing potential only –D84)
 - o Realisation of urinary pregnancy test (yes/no)
 - o If no, reason
 - o If yes, result of the test

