7.6.2 Secondary efficacy endpoint

- For the parameters hereafter: Oxford total score on worse eye, OSDI total score, Van Bijsterveld total score, Schirmer test result on worse eye, TBUT total score on worse eye, all ocular dryness symptoms score separately and then globally (total score):
 - For each product, description of the parameter at D0, D35 and D84.
 - For each product, description of the change of the parameter for each time-point (D35-D0 and D84-D0, relative and absolute variation).
 - A mixed ANOVA model (PROC MIXED) for repeated measures will be fitted to raw data, including the factor treatment as fixed (2 levels), time as fixed (3 levels: D0, D35 and D84), and product by time interaction, as well as the patient effect as random. From this model, the contrasts of interest will be built on the adjusted means:
 - To test whether each change from baseline (D35-D0 and D84-D0) differ significantly from 0 by product.
 - To test whether the products differ significantly for each change from baseline (D35-D0 and D84-D0).
 - The underlying assumptions (normality and homoscedasticity) will be checked using Shapiro-Wilk test and graphical representations of the residuals. In case of strong deviation, a non-parametric approach will be performed.
- For OSDI parameter, the different scores will be classified into the following categories:
 - OSDI None: OSDI (0 - <13)
 - OSDI Mild: OSDI (13 - <23)
 - OSDI Moderate: OSDI (23 - <33)
 - OSDI Severe: OSDI (33 - <100)

The parameter will be described at D0, D35 and D84 (with frequency and percentage)

A comparison of the different categories between products at D0, D35 and D84 will be performed, treatments groups will be compared with a Chi2 test.

- For the parameters hereafter: evaluation of performance by the patient, evaluation of performance for the investigator and frequency of use of the product:
 - The parameter will be described at D0, D35 and D84 (with frequency and percentage)
 - A comparison of the parameter between products at D35 and D84 will be performed: for the evaluation of performance by the patient and by the investigator, and for

frequency of use of the products, treatments groups will be compared with a Chi2 test.

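### The SAP does not produce the protocol's secondary endpoint of mean frequency of use over 84 days, and neither document says how use is collected

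*Protocol*

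**What the plan says.** **Endpoint.** The protocol synopsis and section 6.1.3.2 list "Evaluation of the average frequency of use during 84 days for DM05 and Optive™" among the secondary criteria. Section 6.1.4.1 gives a measurement method for the staining scores, OSDI, Schirmer, TBUT, symptoms and global performance. It gives none for frequency of use.

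**Daily log.** Protocol 6.1.4.2 states: "A daily-log will be given to the subject at each visit in order to write eventual concomitant treatments or adverse events". The selection, D0 and D35 procedures in section 6.4.1 repeat that purpose: "as well as a daily log to write eventual concomitant treatments and adverse events". The protocol schedule (6.1.5) has the row "Distribution of a daily-log" but no row for use of the product. The SAP schedule (3.5) has neither.

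**SAP.** Section 7.5, under "Product and document dispensation (D35 and D84", lists average posology, frequency of use and a precision field for each. Section 7.6.2 groups frequency of use with the two performance ratings and says: "The parameter will be described at D0, D35 and D84 (with frequency and percentage". It continues: "A comparison of the parameter between products at D35 and D84 will be performed", by Chi2 test. Section 4.1.2 extends the between-product comparison to D0, and the planned tables in section 9.1 show frequency of use at D0, D35 and D84. Section 5.3 records no change from the protocol's statistics.

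**Accountability.** Protocol section 11 asks the monitor to verify "products accountability records against record of administrated doses in the CRF". No section defines that dose record.

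**The concern.** The endpoint is an average over the whole treatment period. The planned analysis is two separate cross-tabulations, at D35 and at D84. A Chi2 test on categories gives no mean, no difference in means and no confidence interval, and it ignores the ordering of the frequencies. Nothing combines the two visits within a patient. The D0 description and comparison refer to a time when no study product has been used.

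Patients choose their own frequency within a permitted range and know which product they have (protocol 6.1.2). Someone reading the D35 non-inferiority result will want to know whether the two products were used equally often up to D35. A table of categories with a p-value answers that poorly, and an undescribed data source makes any answer hard to rely on.

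**Working it through.** **1. The plan's own figure.** Neither document gives a sample size, power or target for frequency of use. The only sample size is for the primary endpoint (margin 2, SD 2.5, two-sided 95% CI). By noncentral t, 34 per group gives 90.2% power, and 68 / (1 - 0.15) = 80. It reproduces, and nothing below depends on it.

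**2. Following the endpoint from definition to output.**
- Definition: average over 84 days, by product (protocol 6.1.3.2).
- Measurement method: none in protocol 6.1.4.1.
- Schedule row: none in protocol 6.1.5 or SAP 3.5.
- Visit procedure: the D35 and D84 lists in protocol 6.4.1 mention returned product and the completed log, but no question about instillations.
- Value available: frequency of use at D35 and at D84 (SAP 7.5).
- Derivation: none in SAP 4.3.
- Analysis: categories by visit, Chi2 at D35 and D84 (SAP 7.6.2).
- D0: described in SAP 4.1.2, 7.6.2 and 9.1. Compared between arms in 4.1.2 but not in 7.6.2, so the SAP also disagrees with itself.

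The protocol's general model for quantitative data (7.1.3) does not fill the gap. It has three time levels including D0 and tests change from baseline, and this variable has no baseline.

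**3. Could the two visit values be combined?** If each covers the time since the previous visit (an assumption, as the documents do not say), they span the period:
- D0 to D35: 35 days = 5 weeks.
- D35 to D84: 84 - 35 = 49 days = 7 weeks.
- With the visit windows (±3 and ±7 days), the second interval runs from 77 - 38 = 39 days to 91 - 32 = 59 days.

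An average can therefore be formed, but the intervals are unequal and the weighting is not stated.

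**4. How much the weighting matters.** Time-weighted mean = (d1 × f1 + d2 × f2) / (d1 + d2). Take the widest permitted change, f1 = 4 and f2 = 6 times a day; the unweighted mean is 5.00.
- Nominal dates: (35 × 4 + 49 × 6) / 84 = 434 / 84 = 5.17, a difference of 0.17.
- Reversed (6 then 4): (210 + 196) / 84 = 4.83, again a difference of 0.17.
- Visits at days 32 and 91: (32 × 4 + 59 × 6) / 91 = 482 / 91 = 5.30, a difference of 0.30.
- Visits at days 38 and 77: (38 × 4 + 39 × 6) / 77 = 386 / 77 = 5.01, a difference of 0.01.

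The choice has a small effect for a single patient. It still has to be fixed in advance.

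**5. Could returned product stand in?** Protocol 6.2.1.1 allows 1 to 2 drops per eye, 4 to 6 times a day. Frequency varies 6 / 4 = 1.5-fold and drops per instillation 2 / 1 = 2-fold. A use of 6 drops per eye per day fits 6 × 1 or 4 × 1.5 (averaged over instillations). A use of 8 drops fits 4 × 2 or 6 × 1.33. The amount used does not identify the frequency.

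**The case against.** The best defence is that use data are collected. SAP 7.5 lists four fields at both follow-up visits, which could together cover all 84 days, and protocol section 11 refers to a dose record in the CRF that may be exactly these fields. The endpoint is secondary and plays no part in the primary model or the pass/fail criterion. That stands, and it limits the size of the point. It does not supply the missing derivation, the data source or a reason for the D0 entries.

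Several stronger readings are tempting and are not supported:
- *No daily record exists.* The log template and CRF pages are not in the documents. Only the log's stated purpose is known.
- *The D35 and D84 values are patient recall.* Neither document says so, nor that the CRF dose record is daily.
- *An 84-day average cannot be formed.* Step 3 shows that it could be, under a stated assumption. The gap is the undefined rule.
- *Use varies threefold.* The range of 1 × 4 = 4 to 2 × 6 = 12 drops per eye per day concerns drops. The endpoint is frequency, which varies 1.5-fold.
- *Unequal use could mask inferiority, and a diary would settle it.* Both arms have the same permitted regimen, and the documents give no reason to expect a difference. A diary is still self-report by unblinded patients, and a count of instillations would not record drops.

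**Conclusion.** The point holds for the analysis and for the description of data collection. As written, the SAP yields two categorical tables with Chi2 tests, and a D0 table with no meaningful content. It does not yield the average that the protocol names, and no section states where the frequency comes from.

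The consequence is limited to one secondary endpoint and to the context it gives the D35 result. The primary analysis runs unchanged. At nominal visit dates the choice of weighting is worth at most 0.17 instillations a day per patient, and up to 0.30 at the edges of the visit windows. Both figures assume that frequency stays within 4 to 6 a day and that each visit value describes the interval since the previous visit. The weightier losses are the absent derivation and the absence of an estimate with a confidence interval.

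**What to change.** **SAP 4.1.2, 4.3 and 7.6.2, before database lock**
- Define mean instillations per day over D0-D35, and a time-weighted mean over D0-D84 using each patient's actual interval lengths (nominally 35 and 49 days). State the rule for a patient without a D84 value.
- Compare arms as a quantitative variable, as a difference in means with a 95% CI, in place of the Chi2 test.
- Delete the D0 description and comparison for this variable, and the matching D0 entries in section 9.1.
- Show the D0-D35 mean by arm beside the primary result as context. Do not adjust for it: use arises after randomisation and is part of how each product performs.

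**Data source.** State what the frequency field holds, what period it covers and who supplies it. Say whether it is the dose record named in protocol section 11. Add it to both schedules. If the field holds only classes, so that no mean can be calculated, rename the endpoint as reported frequency at D35 and at D84.

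**Optional, where still feasible.** Add number of instillations per day to the log already handed out at D0 and D35.

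**Cost.** The SAP changes cost almost nothing, and the schedule row is a small protocol edit. The log entry adds a small daily burden for patients and some data entry, and it remains unblinded self-report.

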6.1.5 Timing for assessing and recording the variables

Procedure	Visit 1 Selection visit (D-14 to D-7)	Visit 2 Day 0	Visit 3 Day 35 ± 3 days	Visit 4 Day 84 ± 7 days
	Wash-out period			
	Treatment period			
Written informed consent	●			
Checking of the inclusion and exclusion criteria	●	●		
Medical history, previous and concomitant treatments, demographic data	●			
Urinary pregnancy test for female subjects with childbearing potential		●		●
Distribution of Hydrabak® (NaCl 0.9%)	●			
Inclusion and random assignment		●		
OSDI score	●	●	●	●
Global ocular staining (Oxford score)	●	●	●	●
Schirmer test	●	●	●	●
TBUT	●	●	●	●
Van Bijsterveld score		●	●	●
Symptoms evaluation by the patient		●	●	●
Treatment performance evaluation by the patient and the investigator			●	●
Distribution of treatments by a third person		●	●	
Distribution of a daily-log	●	●	●	
Adverse events recording		●	●	●
Concomitant medication		●	●	●

6.1.6 Equipment to be used for assessing, recording and analysing variables and arrangements for monitoring maintenance and calibration

Each investigator will use his own slit lamp. Dyes (Fluoresceine Faure 0.5% SDU, Lissamine green) and Schirmer strips will be given by the Sponsor.

